8.1.7 Withdrawn subjects

If a subject is withdrawn from the trial, the investigator must aim to undertake procedures similar to those for Visit 26 as soon as possible. The subject should also have the follow-up contact performed, if possible. The subjects should be requested to return all used, partly used and unused trial product.

The end-of-trial form must be completed, and final drug accountability must be performed even if the subject is not able to come to the trial site. A withdrawal session must be made in the IV/WRS. The case book must be signed.

Although a subject is not obliged to give his/her reason(s) for withdrawing from a trial, the investigator must make a reasonable effort to ascertain the reason(s), while fully respecting the subject's rights. Where the reasons are obtained, the primary reason for not completing the trial must be specified on the end-of-trial form in the eCRF.

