8.4 Assessments for safety

8.4.1 Hypoglycaemic episodes

Blood glucose should always be measured and recorded when a hypoglycaemic episode is suspected.

All plasma glucose values:

- ≤ 3.9 mmol/L (70 mg/dL) or
- > 3.9 mmol/L (70 mg/dL) when they occur in conjunction with hypoglycaemic symptoms

- should be recorded by the subject. These must be transcribed into the eCRF (hypoglycaemic episode form) throughout the trial from Visit 2 to the follow-up phone contact 27.

The record should include the following information:

- Date and time of hypoglycaemic episode
- The plasma glucose level before treating the episode (if available)
- Whether the episode was symptomatic
- Whether the subject was able to treat him/herself
- Date and time of last trial insulin and metformin administration prior to episode
- Dose of last trial insulin and metformin administration prior to episode
- Date and time of last main meal prior to episode. The definition for ‘main meal’ will be according to the investigator’s discretion.
 - Whether the episode occurred in relation to physical activity
 - Any sign of fever or other disease
 - Whether the subject was asleep when the episode occurred
 - If yes, whether the symptoms of the episode woke up the subject

The answer to the question: “Was subject able to treat him/herself?” must be answered “No” for an episode requiring assistance of another person to actively administer carbohydrate, glucagon, or take other corrective actions. Plasma glucose concentrations may not be available during an event, but neurological recovery following the return of plasma glucose to normal is considered sufficient evidence that the event was induced by a low plasma glucose concentration.

Oral carbohydrates should not be given if the subject is unconscious.

If the question “Was subject able to treat him/herself?” is answered “No”, the following information should be recorded:

- Who assisted in the treatment of the hypoglycaemic episode (i.e. family/friend/co-worker or similar, paramedic, doctor or other, please specify)
- Where the treatment was administered (i.e. at home/at friends/at work or similar, in an ambulance, emergency room/hospital or other, please specify)
- Type of treatment provided by other person (i.e. oral carbohydrates, glucagon, IV glucose or other, please specify)
- Were symptoms alleviated after administration of treatment?

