- Factors contributing to the episode (i.e. physical activity, missed meal, diet changed, medication error (i.e. overdose, mix-up between products), miscalculation of insulin dose, other factors not listed, please specify or none)
- Did the subject experience seizure?
- Was the subject unconscious/comatose?
- Did the subject experience any of the following symptoms¹⁷?
 - Autonomic: sweating, trembling, hunger or palpitations
 - Neuroglycopenic: confusion, drowsiness, speech difficulty, visual disturbances, odd behaviour, impaired balance or incoordination

- General malaise: headache or malaise
 - Did the subject experience other symptoms? Please specify
 - Description of the episode, if applicable

A hypoglycaemic episode form must be filled in for each hypoglycaemic episode. If the hypoglycaemic episode fulfils the criteria for an SAE then an AE form and a safety information form must also be filled in, see Section [12](#).

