12.1 Definitions

Adverse event

An AE is any untoward medical occurrence in a subject administered a product, and which does not necessarily have a causal relationship with this treatment.

An AE can therefore be any unfavourable and unintended sign (including an abnormal laboratory finding), symptom or disease temporally associated with the use of a product, whether or not considered related to the product.

An AE includes:

- A clinically significant worsening of a concomitant illness.
- A clinical laboratory adverse event (CLAE): a clinical laboratory abnormality which is clinically significant, i.e. an abnormality that suggests a disease and/or organ toxicity and is of a severity that requires active management. Active management includes active treatment or further investigations, for example change of medicine dose or more frequent follow-up due to the abnormality.

The following should **not** be reported as AEs:

- Pre-existing conditions, including those found as a result of screening procedures (pre-existing conditions should be reported as medical history or concomitant illness).
- Pre-planned procedures unless the condition for which the procedure was planned has worsened from the first trial related activity after the subject has signed the informed consent.
- Non-serious hypoglycaemia is an AE, but is reported on a hypoglycaemic episode form instead of on an AE form, see Section [8.4.1](#).

The following three definitions are used when assessing an AE:

- **Severity**
 - **Mild** - no or transient symptoms, no interference with the subject's daily activities.
 - **Moderate** - marked symptoms, moderate interference with the subject's daily activities.
 - **Severe** - considerable interference with the subject's daily activities; unacceptable.

- **Causality**

Relationship between an AE and the relevant trial product(s):

- **Probable** - Good reason and sufficient documentation to assume a causal relationship.
- **Possible** - A causal relationship is conceivable and cannot be dismissed.
- **Unlikely** - The event is most likely related to aetiology other than the trial product.

- **Final outcome**
- **Recovered/resolved** - The subject has fully recovered, or by medical or surgical treatment the condition has returned to the level observed at the first trial-related activity after the subject signed the informed consent.

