12.2 Reporting of adverse events

All events meeting the definition of an AE must be collected and reported. This includes events from the first trial-related activity after the subject has signed the informed consent until the end of the post-treatment follow-up period (i.e. Visit 1 to P 27). The events must be recorded in the applicable eCRF forms in a timely manner, see timelines below and [Figure 12-1](#).

During each contact with the trial site staff, the subject must be asked about AEs and technical complaints, for example by asking: “Have you experienced any problems since the last contact?”

All AEs, either observed by the investigator or subject, must be reported by the investigator and evaluated. Novo Nordisk assessment of expectedness is performed according to the following reference documents:

- Company core data sheet (CCDS) for NovoMix[®] 30, current version and any updates thereto

All AEs must be recorded by the investigator on an AE form. The investigator should report the diagnosis, if available. If no diagnosis is available, the investigator should record each sign and symptom as individual AEs using separate AE forms.

For SAEs, a safety information form must be completed in addition to the AE form. If several symptoms or diagnoses occur as part of the same clinical picture, one safety information form can be used to describe all the SAEs.

MESIs, regardless of seriousness, must be reported using both the AE form and the safety information form.

The AE form for a non-serious AE not fulfilling the MESI criteria should be signed when the event is resolved or at the end of the trial.

Timelines for initial reporting of AEs:

The investigator must complete the following forms in the eCRF within the specified timelines:

- **SAEs:** The AE form **within 24 hours** and the safety information form **within 5 calendar days** of the investigator's first knowledge of the SAE.

Both forms must be signed within 7 calendar days from the date the information was entered in the eCRF.

- **Non-serious AE fulfilling the MESI criteria:** The AE form, and safety information form **within 14 calendar days** of the investigator's first knowledge of the event.

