12.6 Precautions and/or overdose

Treatment with insulin may result in hypoglycaemia. A specific overdose for insulin cannot be defined. However, hypoglycaemia may develop over sequential stages if too high doses relative to the patient's requirement are administered. Symptoms may occur suddenly and include cold sweat, nervousness or tremor, anxious feelings, unusual tiredness, confusion, difficulty in concentrating, excessive hunger, temporary vision changes, headache, nausea and palpitation. Severe hypoglycaemia may lead to unconsciousness and even death.

Hypoglycaemia should be treated according to best available medical practice at the discretion of the investigator. Mild hypoglycaemic episodes can be treated by oral administration of glucose or sugary products. It is therefore recommended that the diabetic patient always carries sugar containing products. Severe hypoglycaemic episodes, where the patient has become unconscious, can be treated with glucagon (0.5 to 1 mg) given intramuscularly or subcutaneously, by a trained person, or with glucose given intravenously by a healthcare professional. Glucose must be given intravenously, if the patient does not respond to glucagon within 10 to 15 minutes. Upon regaining consciousness, administration of oral carbohydrates is recommended for the patient in order to prevent a relapse.

If hypoglycaemia is caused by an overdose, the event should be reported as a MESI.

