17.4.1.2 Safety endpoints

All safety endpoints will be summarised and analysed using the safety analysis set. Unless otherwise specified safety endpoints will be analysed by descriptive statistics only.

Adverse events

All AEs will be coded using the most recent version of the MedDRA coding. A TEAE is defined as an event that has onset date (or increase in severity) on or after the first day of exposure to trial product and no later than 7 days after the last day on trial product.

TEAEs are summarised descriptively and displayed in terms of the number of subjects with at least one event (N), the percentage of subjects with at least one event (%), the number of events (E) and the event rate per 1000 years of exposure (R)

Summaries of TEAEs and of serious TEAEs will be presented as an overview including all AEs, serious AEs, number of deaths, AEs by severity, AEs by relation to treatment and AEs leading to withdrawal.

Furthermore summary tables based on system organ class and preferred terms are made for:

- All TEAEs
- Serious TEAEs
- Possibly or probably related TEAEs
- Severe, moderate and mild TEAEs
- TEAEs with preferred term that are experienced by at least 5% of the subjects in any treatment arm or by at least 5% of all subjects
- TEAEs leading to withdrawal

Definition of Hypoglycaemia

Treatment emergent: hypoglycaemic episodes will be defined as treatment emergent if the onset of the episode occurs on or after the first day of trial product administration, and no later than 7 days after the last day on trial product.

Nocturnal hypoglycaemic episodes: are episodes with time of onset between 00:01 and 05.59 both inclusive.

[figure not shown]
Hypoglycaemic episodes are classified according to the Novo Nordisk classification of hypoglycaemia (see [Figure 17–1](#)) and the ADA classification of hypoglycaemia (see [Figure 17–2](#)).

Novo Nordisk classification of hypoglycaemia

In normal physiology, symptoms of hypoglycaemia occur below a plasma glucose level of 3.1 mmol/L (56 mg/dL)²¹. Therefore, Novo Nordisk has included hypoglycaemia with plasma glucose levels below this cut-off point in the definition of blood glucose (BG) confirmed hypoglycaemia.

Novo Nordisk uses the following classification in addition to the ADA classification:

- Severe hypoglycaemia according to the ADA classification²².

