18.1 Benefit-risk assessment of the trial

BIAsp 30 has been on the market for more than 10 years and has been exposed to several million subjects. BIAsp 30 has well-known safety profiles and offers a treatment regimen presumed to be better than or equal to the treatment subjects received at the time of entering the trial.

All subjects included in the trial will be treated with BIAsp 30 TID or BIAsp 30 BID in addition to metformin in order to improve glycaemic control. The trial insulin will be titrated by the investigator. Titration will be performed according to titration algorithms for BIAsp 30 in order to achieve the pre-meal SMPG target 4.4–6.1 mmol/L (80–110 mg/dL).

The most frequently reported adverse reaction during treatment with BIAsp 30 is hypoglycaemia. The frequencies of hypoglycaemia vary with patient population, dose regimens and level of glycaemic control. However, the investigator will explain to the subject how to check their blood sugar with the blood glucose meter provided by Novo Nordisk and to take precautions.

The subjects will have to spend some extra time, as additional visits to the clinic are required and some of the tests performed during the trial are outside normal practice. However, the anticipated benefit of participating in this trial, i.e. improved glycaemic control due to the closer and more frequent assessments of the subject's diabetes and intensified diabetes treatment and the close contact with the trial site (including physical examinations) is expected to outweigh the risk for these subjects who have already failed their previous diabetes treatment.

Subjects participating in the proposed trial must have an HbA_{1c} value between 7.5% and 10.0%, since it is expected that this population will most likely benefit from intensification of premixed insulin treatment with BIAsp 30. All subjects in the proposed trial will have their blood glucose monitored regularly, and will receive BIAsp 30 TID or BID. Thus, their diabetes treatment and glycaemic control will most likely be optimised during the trial period.

Participation in this trial can lead to an increase in subjects' understanding regarding the importance of glucose control.

An internal Novo Nordisk safety committee for BIAsp 30 will perform ongoing safety surveillance during the trial.

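### Withdrawals due to non-serious hypoglycaemia have no stated route into the planned table of adverse events leading to withdrawal

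*Combined protocol and SAP*

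**What the plan says.** **Which form is used.** Section 12.1, in its list of things not to be reported as AEs, says: "Non-serious hypoglycaemia is an AE, but is reported on a hypoglycaemic episode form instead of on an AE form". Section 8.4.1 adds a second route for serious episodes: "If the hypoglycaemic episode fulfils the criteria for an SAE then an AE form and a safety information form must also be filled in". Section 12.6 adds a third: "If hypoglycaemia is caused by an overdose, the event should be reported as a MESI". Section 12.2 then says of such events: "MESIs, regardless of seriousness, must be reported using both the AE form and the safety information form". Section 12.2 also has a general rule that sends every AE to an AE form and states no exception for hypoglycaemia.

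**What the episode record holds.** Section 8.4.1 introduces its list with "The record should include the following information". The list covers timing, glucose value, symptoms, self-treatment, last dose and last meal, physical activity, illness and sleep. For episodes needing assistance it adds who helped, where, how, contributing factors, seizure, consciousness and symptoms.

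**What is tabulated.** Section 17.4.1.2 plans a TEAE overview that includes AEs leading to withdrawal, and a table by system organ class and preferred term of "TEAEs leading to withdrawal". Hypoglycaemia is summarised separately, as subjects, percentages, events and rates by classification.

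**Reason for withdrawal.** Under Section 8.1.7, where the reason is obtained, "the primary reason for not completing the trial must be specified on the end-of-trial form in the eCRF".

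**The concern.** Comparing the safety of three with two daily injections is a stated objective, and Section 18.1 says: "The most frequently reported adverse reaction during treatment with BIAsp 30 is hypoglycaemia". How many subjects gave up each regimen because of hypoglycaemia is therefore a basic tolerability comparison. Section 17.3 names adverse events among the main expected reasons for withdrawal.

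The form rules appear to separate this event from the table meant to show it. A subject who leaves after repeated non-serious episodes may have no AE form for them, and the planned hypoglycaemia outputs count episodes without saying which ended participation. The comparison between arms of withdrawals for adverse events would then be incomplete for the event of most interest.

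The two form rules also pull apart. One site could follow Section 12.1 and another Section 12.2, so capture of the same event could differ between sites.

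**Working it through.** There is no plan figure to reproduce for this point. The check follows each kind of episode from form to table, then sets a scale.

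**1. Route by type of episode**

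| Type of hypoglycaemia | Form(s) | Reaches the AE form? |
|---|---|---|
| Serious | Episode form, AE form and safety information form (8.4.1) | Yes |
| Caused by overdose, hence MESI | AE form and safety information form, whatever the seriousness (12.6, 12.2) | Yes |
| Non-serious, not MESI | Episode form in place of AE form (12.1) | No under 12.1; yes under the general rule in 12.2 |

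The third row can include some severe episodes. In Section 17.4.1.2, severe under the ADA classification means needing another person's active help. That is not in itself one of the SAE criteria in Section 12.1, although such an episode may qualify as an important medical event.

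**2. Link from episode to withdrawal.** None of the items listed in Section 8.4.1 concerns withdrawal or action taken with trial product.

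**3. Source of the withdrawal table.** Section 17.4.1.2 does not name it. Three features point to AE forms:
- The TEAE outputs are split by severity grade and by relation to treatment. The listed episode items collect neither.
- TEAE rates are per 1000 years of exposure and hypoglycaemia rates per 100 years, which suggests two data streams.
- Hypoglycaemia has its own definitions and its own summaries within that section.

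**4. Both readings**
- *Table built from AE forms:* withdrawals in the third row are left out if sites follow Section 12.1.
- *Table also built from episode records:* the TEAE definition rests on timing and does not exclude these episodes, but no listed item identifies those that led to withdrawal.

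On either reading, the plan does not say how these withdrawals are counted.

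**5. Other outputs.** The hypoglycaemia summaries give numbers, percentages, events and rates. The negative binomial model analyses episode counts. Neither reports withdrawals. The end-of-trial form holds one primary reason, where obtained, and nothing in the text ties it to an episode or to this table.

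**6. Scale.** Inputs from Section 6.1: 426 to be randomised, 340 expected to complete.
- Expected non-completers: 426 − 340 = 86, and 86/426 = 20.2%.
- The share due to non-serious, non-MESI hypoglycaemia is not given. As an assumption, with a range that includes zero:

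| Assumed share of the 86 | Subjects | Share of 426 |
|---|---|---|
| 0% | 0 | 0% |
| 5% | 4.3 | 1.0% |
| 10% | 8.6 | 2.0% |
| 15% | 12.9 | 3.0% |

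**The case against.** **The omission is inferred.** The table's source is not stated, Section 12.1 itself calls non-serious hypoglycaemia an AE, and the TEAE definition would admit it. Section 17 also allows a more technical SAP, which might settle the source; no separate one is among the documents. This stands, and it is why the conclusion is put as the most natural reading. It does not remove the gap, because the alternative reading lacks a listed item to work from.

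**The forms cannot be inspected.** Section 8.4.1 lists what the record should include, which need not be every field, and the plan lists no withdrawal field for the AE form either. This also stands: a reader might infer that the episode form certainly lacks such a field, and the documents do not show that. But the plan commits to a table of TEAEs leading to withdrawal, so that attribute must be available for the TEAEs tabulated. It makes no comparable commitment for episodes.

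**An excess of hypoglycaemia would still be seen.** A reader might infer that a difference between arms is hidden. The documents do not support that. Treatment-emergent episodes are summarised by both classifications, severe or BG-confirmed episodes get a rate ratio with confidence interval and p-value, and withdrawn subjects count as non-responders in both composite endpoints that involve hypoglycaemia. What stays unclear is one descriptive attribution: who withdrew because of the episodes.

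**Missing data.** Section 17.3 calls the missing-at-random assumption questionable for adverse-event withdrawals, so a reader might infer that the sensitivity analyses suffer. They do not. The repeated-measures model, the LOCF analysis and the control-based imputation make no use of the reason for withdrawal.

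**Conclusion.** The point holds in a limited form. Under Section 12.1 as written, withdrawals due to hypoglycaemia that is neither serious nor a MESI would most naturally be absent from the withdrawal table, and no planned hypoglycaemia summary recovers them by arm. The plan should also not leave the form rules in Sections 12.1 and 12.2 in conflict.

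It would go too far to say that the table omits withdrawals due to hypoglycaemia in general, since serious and overdose-related episodes have an explicit route to the AE form.

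The size is unknown. The range of 0 to 13 subjects rests on an assumed share of 0–15% of expected non-completers, and on the table using AE forms alone with sites following Section 12.1. The effect is on the completeness of a descriptive safety comparison. The primary and missing-data analyses do not change. This is a modest defect that is cheap to correct.

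**What to change.** 1. In Section 12.1, keep the episode form for non-serious hypoglycaemia, but require an AE form as well for any hypoglycaemic episode, or series of episodes, that leads to withdrawal, whether or not serious. Repeat the rule in Section 8.4.1.
2. In Section 12.2, qualify the general AE-form rule so that it agrees with Section 12.1.
3. In Section 17.4.1.2, state the source of the withdrawal table, and count these events by arm in the AE overview and in the table itself.

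The wording should cover a series of episodes. A yes/no item on each episode record would not be enough on its own, because the reason for leaving may be repeated episodes rather than any single one.

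The cost is a sentence in the reporting rules, a consistent programming rule and a few extra AE forms. The count of withdrawals for adverse events may come out slightly higher. If the eCRF already records this link, it is enough to say so in the plan, name it as the table's source and reconcile Sections 12.1 and 12.2.

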8.2 Subject related information

8.2.1 Concomitant illness and medical history

A **concomitant illness** is any illness that is present at the start of the trial (i.e. at the screening visit) or found as a result of screening procedures. The disease under investigation (type 2 diabetes) is not considered as a concomitant illness and it is captured under diagnosis of diabetes.

Any change to a concomitant illness should be recorded during the trial. A clinically significant worsening of a concomitant illness must be reported as an AE.

Medical history is a medical event that the subject has experienced in the past. Only medical history considered relevant by the investigator should be reported.

The information collected for concomitant illness and medical history should include diagnosis, date of onset and date of resolution or continuation, as applicable.

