- **Recovering/resolving** - The condition is improving and the subject is expected to recover from the event. This term is only applicable if the subject has completed the trial or has died from another AE.
- **Recovered/resolved with sequelae** - The subject has recovered from the condition, but with lasting effect due to a disease, injury, treatment or procedure. If a sequela meets an SAE criterion, the AE must be reported as an SAE.
- **Not recovered/not resolved** - The condition of the subject has not improved and the symptoms are unchanged, or the outcome is not known.
- **Fatal** - This term is only applicable if the subject died from a condition related to the reported AE. Outcomes of other reported AEs in a subject before he/she died should be assessed as “recovered/resolved”, “recovering/resolving”, “recovered/resolved with sequelae” or “not recovered/not resolved”. An AE with fatal outcome must be reported as an SAE.
- **Unknown** - This term is only applicable if the subject is lost to follow-up.

Serious adverse event

A serious adverse event (SAE) is an experience that at any dose results in any of the following:

- Death.
 - A life-threatening^a experience.
 - In-patient hospitalisation^b or prolongation of existing hospitalisation.
 - A persistent or significant disability or incapacity^c.
 - A congenital anomaly or birth defect.
 - Important medical events that may not result in death, be life threatening^a or require hospitalisation^b may be considered an SAE when - based on appropriate medical judgement - they may jeopardise the subject and may require medical or surgical intervention to prevent one of the outcomes listed in the definition of SAE^d.
- Suspicion of transmission of infectious agents via the trial product must always be considered an SAE.

^a The term “life threatening” in the definition of SAE refers to an event in which the subject was at risk of death at the time of the event. It does not refer to an event which hypothetically might have caused death if it was more severe.

- b The term “hospitalisation” is used when a subject:
- Is admitted to a hospital or in-patient, irrespective of the duration of physical stay, or
 - Stays at the hospital for treatment or observation for more than 24 hours

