Medical judgement must always be exercised, and when in doubt, the hospital contact should be regarded as a hospitalisation. Hospitalisations for administrative, trial related and social purposes do not constitute AEs and should therefore not be reported as AEs or SAEs. Hospital admissions for surgical procedures, planned before trial inclusion, are not considered AEs or SAEs.

- c A substantial disruption of a subject's ability to conduct normal life functions (e.g. following the event or clinical investigation the subject has significant, persistent or permanent change, impairment, damage or disruption in his/her body function or structure, physical activity and/or quality of life).
- d For example intensive treatment in an emergency room or at home of allergic bronchospasm, blood dyscrasias or convulsions that do not result in hospitalisation, or development of drug dependency or drug abuse.

Note: The seriousness criterion “important medical event” is not the same as the term “Medical event of special interest” (MESI).

Non-serious adverse event

A non-serious AE is any AE which does not fulfil the definition of an SAE.

Medical event of special interest

A medical event of special interest (MESI) is an event which, in the evaluation of safety, has a special focus. A MESI is an AE (SAE or non-serious AE) which fulfils one or more of the below defined MESI criteria.

Medication errors concerning trial products:

- Administration of wrong drug.
Note: Use of wrong DUN(s) is not considered a medication error unless it results in administration of wrong drug.
- Wrong route of administration, such as intramuscular instead of subcutaneous.
- Administration of an overdose with the intention to cause harm (e.g. suicide attempt).
- Accidental administration of a lower or higher dose than intended. That is a dose lower or higher than the intended dose; however the administered dose must deviate from the

intended dose to an extent where clinical consequences for the trial subject were likely to happen as judged by the investigator, although they did not necessarily occur.

Technical complaint

A technical complaint is any written, electronic, or oral communication that alleges product (medicine or device) defects. The technical complaint may be associated with an AE, but does not concern the AE itself.

Examples of technical complaints:

- The physical or chemical appearance of trial products (e.g. discoloration, particles or contamination)

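### Section 12.1: note b exempts pre-planned surgical admissions from AE and SAE status without the worsening exception that the AE definition in the same section applies

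*Combined protocol and SAP*

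**What the plan says.** Both rules are in Section 12.1 (Definitions).

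- **Adverse event definition.** The list of things not to be reported as AEs includes "Pre-planned procedures unless the condition for which the procedure was planned has worsened from the first trial related activity after the subject has signed" consent. The exemption is therefore conditional and lapses when the condition worsens.
- **Serious adverse event definition, note b.** This note explains the hospitalisation criterion and ends: "Hospital admissions for surgical procedures, planned before trial inclusion, are not considered AEs or SAEs". No condition is attached, and there is no reference back to the AE definition.

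Three other provisions bear on the point.

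- An AE is serious if it results in "In-patient hospitalisation" "or prolongation of existing hospitalisation". Note b counts any admission, however short.
- Section 8.2.1 states: "A clinically significant worsening of a concomitant illness must be reported as an AE". The AE definition in Section 12.1 includes the same category.
- Note b also says that "when in doubt, the hospital contact should be regarded as a hospitalisation".

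**The concern.** A subject may enter the trial with an operation already planned, and the condition may then worsen after consent. Under the AE definition the exemption no longer applies. Under note b the surgical admission is still outside both AE and SAE status. Two sites could classify identical events differently, each following a sentence in the same section.

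What is at stake is the serious label and what follows from it:

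- **Initial reporting (Section 12.2).** An SAE needs the AE form within 24 hours and the safety information form within 5 calendar days. A non-serious AE that is not a medical event of special interest has no such deadline there; its form is signed at resolution or at the end of the trial.
- **Follow-up (Section 12.3).** SAE follow-up information is due within 24 hours. Follow-up of a non-serious AE can stop at the end of the follow-up period.
- **Tabulation (Section 17.4.1.2).** Serious TEAEs have their own summaries.

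**Working it through.** No calculation applies: the point rests on the wording of two rules, not on a sample size, power or event figure. The check is to apply both rules to each type of case and then look for a provision that settles any difference.

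**Case 1: surgery planned before inclusion, condition stable.** The AE definition exempts the procedure and note b exempts the admission. The rules agree.

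**Case 2: condition worsened after consent, surgery goes ahead exactly as booked.** The AE definition withdraws the exemption. The worsening is an AE, also under Section 8.2.1 if it is clinically significant. The admission would have happened anyway, so it is doubtful that the worsening resulted in hospitalisation. The rules can be read together: the worsening is the AE, and the booked admission adds nothing to its seriousness.

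**Case 3: condition worsened after consent, and the worsening leads to the admission, brings it forward or changes it.** The AE definition again makes the event reportable. The event now results in an in-patient stay, which meets the hospitalisation criterion. Note b, read literally, still says that the admission is neither an AE nor an SAE, because the surgery was planned before inclusion. The rules conflict.

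**Does another provision resolve Case 3?**

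- The when-in-doubt sentence in note b concerns whether a hospital contact is a hospitalisation. It does not address planned surgery, and the unconditional exemption comes after it.
- Section 8.2.1 keeps the worsening reportable as an AE but is silent on its seriousness.
- Exclusion criterion 9 (Section 6.3) removes only planned coronary, carotid or peripheral artery revascularisation. Subjects with other planned surgery can be randomised.
- Sections 12.2 and 12.3 set timelines once an event has been classified. They do not say how to classify it.

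None of these sets an order of precedence.

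**Effect on outputs.** Section 17.4.1.2 defines a TEAE by onset, or increase in severity, from the first day of exposure to 7 days after the last day on trial product. A Case 3 event in that window could be missing from the serious TEAE tables. One between consent and first dose would affect only SAE reporting. The tables are descriptive.

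**The case against.** The strongest reply is that the two sentences have different subjects. The AE definition says when a procedure and its condition become reportable. Note b says only that a pre-arranged admission is not itself an event. An SAE must result in hospitalisation, and an admission booked before inclusion does not result from a later worsening. If the worsening causes an earlier or different stay, that stay is arguably no longer the one that was planned, and prolongation is a separate criterion.

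This stands for Case 2. For Case 3 it needs a reading that the text does not state. Note b's sentence can attach the planning to the procedure as well as to the admission, and on the former reading an operation brought forward is still exempt. Note b also says that such admissions are not AEs, which sits badly with the AE definition once the condition has worsened.

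The reply also rightly limits what can be claimed. A reader might infer three stronger points that the documents do not support:

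- **That the rules are opposites throughout.** They agree whenever the condition is stable.
- **That the event drops out of the sponsor's safety surveillance.** The worsening remains an AE, data entered in the eCRF are available to the sponsor (Section 13.2), and Section 12.7.1 does not confine the safety committee to SAEs. The other seriousness criteria, including important medical events, also still apply.
- **That open-label classification would favour one arm.** Investigators know the regimen, but nothing in the documents suggests that they would apply note b differently by arm, and both arms receive the same product.

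**Conclusion.** Note b is wrong as written, in a narrow respect: it omits the worsening exception that the same section states for pre-planned procedures. The inconsistency matters when a condition worsens after consent and the worsening leads to, brings forward or changes the planned surgical admission. What can then be lost is the serious classification, with its reporting timelines and its place in the descriptive serious TEAE tables. The AE record of the worsening is not lost.

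The size cannot be derived. The documents do not say how many of the 426 planned subjects have surgery scheduled, or how often such conditions worsen, so any count would be guesswork. It is likely to be very small. The primary analysis of HbA1c is unaffected. The conclusion assumes only that a site may read note b literally, which its wording allows.

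**What to change.** Reconcile the two places in Section 12.1. Either add to note b that the exemption does not apply when the condition for which surgery was planned has worsened since the first trial-related activity after consent, in which case the event is an AE and is assessed for seriousness in the usual way; or have note b refer to the limit in the AE definition.

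The change is one clause that extends a rule the sponsor has already written. It adds no procedure or assessment and leaves clinical management as it is. The downside is at most a few more SAE reports.
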